3. Where a subject would have been scheduled to attend clinic at months 8, 16, 24, 32 etc after randomisation, a clinic visit will be performed (with assessments as shown above). If a subject who has permanently discontinued IP is unable to attend clinic then they will be contacted by telephone instead and the telephone contact assessments will be performed.
4. Once it is projected that the target number of MACE events will have been collected, a 3 month window will be defined for conducting the final, face to face visit.
5. Liver function tests: ALT, AST, alkaline phosphatase, bilirubin, GGT.
6. Lipid values (TC, LDLc, HDLc, Tg) to be recorded as available from routine clinical care annually. If results are unavailable, lipids tests are not to be performed for the study.
7. TRIM-D, EQ-5D and study specific questionnaire (details in Section 6.3).
8. See Section 6.2.7.

Section 6.2.1 Cardiovascular Events; footnote added to end of first sentence.*Original text:*

Events referred to the CEC by the investigator as potential endpoints or transient ischemic attacks (TIAs) will not be collected or reported as SAEs, regardless of the adjudication outcome (Section 6.2.2).

Amended text:

Events referred to the CEC by the investigator as potential endpoints or transient ischemic attacks (TIAs) will not be collected or reported as SAEs, regardless of the adjudication outcome (Section 6.2.2).¹

Footnote:

¹ There is one exception to this statement. Per requirement of the Mexican Ministry of Health, all events referred to the CEC by Mexican investigators will also be submitted as SAEs to the Mexican Ministry of Health.

Section 6.2.6 Clinical Laboratory Assessments; text to be inserted at end of sub-section***Lipids***

Where serum lipid tests have been performed as part of the subject's routine clinical care (i.e. not as a study procedure) the most recent results should be recorded at baseline and annually thereafter. The lipid parameters to be recorded are total cholesterol (TC), low density lipoprotein cholesterol (LDLc), high density lipoprotein (HDLc) and triglycerides (Tg).

If any or all of these results are not already available from the subject's records then separate lipid tests should not be performed solely for the study.

Section 6.3.1.1. Treatment Related Impact Measure – Diabetes (TRIM-D)

Original Text:

In order to evaluate satisfaction with treatment and to compare satisfaction across treatment groups, the TRIM-D questionnaire will be self administered by all subjects at baseline and at each 8 month visit (and, to the extent possible, at the time of study completion or withdrawal from the study).

Amended Text:

In order to evaluate satisfaction with treatment and to compare satisfaction across treatment groups, the TRIM-D questionnaire will be self administered by all subjects at baseline (except for subjects whose diabetes is treated by diet and exercise alone) and all subjects at each 8 month visit (and, to the extent possible, at the time of study completion or withdrawal from the study).

Section 8.3.3.1 Primary Comparisons of Interest, second sentence*Original text:*

The primary endpoint will be the time to the first occurrence of MACE over the full duration of the study. A p-value for the primary endpoint will be calculated from a Cox regression model with treatment group as the only covariate for the hypotheses described in Section 8.1.

Amended text:

The primary endpoint will be the time to the first occurrence of MACE over the full duration of the study. A p-value for the primary endpoint will be calculated from a Cox **Proportional Hazards (PH)** regression model with treatment group as the only covariate for the hypotheses described in Section 8.1.

Section 8.3.3.2. Other Comparisons of Interest, insertion of two new sentences:*Original text:*

For other analyses incidence rates will be presented for binary data and summary statistics (mean, median, standard deviation, minimum, and maximum) will be presented for continuous data. Furthermore, summary statistics of change from baseline for HbA1c will be presented along with percent of subjects within ranges of clinical interest (e.g., HbA1c < 7.0%).

Amended text:

For other analyses incidence rates will be presented for binary data and summary statistics (mean, median, standard deviation, minimum, and maximum) will be presented for continuous data. **Time to event endpoints will be evaluated via the p-value from a Cox PH regression model with treatment as the only covariate.** Furthermore, summary statistics of change from baseline for HbA1c will be presented along with percent of subjects within ranges of clinical interest (e.g., HbA1c < 7.0%). **Available lipid data will be summarized for descriptive purposes.**

Section 8.3.6.2. Secondary Endpoint Analysis*Original text:*

- Composite of the proportion of those achieving good control (HbA1c ≤ 7.0%) AND no severe hypoglycaemic incidents AND weight gain <5% at the end of the study would be evaluated utilize nonparametric, covariance-adjusted, extended Mantel-Haenszel tests. Additional analysis will be provided for scheduled visits. Nominal p-values and 95% CIs will be presented for these visits. Time to introduction of prandial insulin in those on basal insulin ± orals anti-hyperglycemic drugs at baseline will be analyzed using PH model / log-rank test and KM method similar to the primary endpoint.

- Composite of microvascular events will be analyzed using a proportional Cox regression model / log-rank test and KM method similar to the primary endpoint.

Amended text:

- Composite of the proportion of those achieving good control ($HbA1c \leq 7.0\%$) AND no severe hypoglycaemic incidents AND weight gain $<5\%$ at the end of the study would be evaluated utilize nonparametric, covariance-adjusted, extended Mantel-Haenszel tests. Additional analysis will be provided for scheduled visits. Nominal p-values and 95% CIs will be presented for these visits. Time to introduction of prandial insulin in those on basal insulin \pm orals anti-hyperglycemic drugs at baseline will be analyzed using **a Cox PH** model ~~/log-rank test~~ and KM method similar to the primary endpoint.
- Composite of microvascular events will be analyzed using a proportional Cox regression model ~~/log-rank test~~ and KM method similar to the primary endpoint.

Section 8.3.6.4. Other Safety Analyses, paragraphs 3, 4 and 5.

Original text:

For SAEs, AEs leading to withdrawal and AEs of special interest occurring after discontinuation of investigational product, the number and percentage of subjects, total number of events, incidence density and event rate will be presented by treatment group and overall at the SOC, High Level Term and Preferred Term (PT) level. Relative Risk for each event and its 95% CI will also be presented. The time to first occurrence of the specific events and the time of the event with respect to the preceding dose of study medication will be summarized.

All cause mortality will be summarized by treatment group and analyzed using PH model similarly as the-primary endpoint.

All events sent to CEC (including TIAs) will be grouped by type based on the standard MedDRA queries that correspond to cardiovascular and cerebrovascular events. Adjudication results will be summarized by event type and treatment group. A by subject listing of these events will be generated. The listing will include seriousness, severity, whether event is a reason for early study drug discontinuation or study withdrawal, and adjudication results.

Pancreatitis events will be adjudicated by the independent Pancreatitis Adjudication Committee. The information for investigator reported pancreatitis events and its adjudication results will be provided.

Amended text:

For SAEs, AEs leading to **permanent IP** withdrawal and AEs of special interest ~~occurring after discontinuation of investigational product~~, the number and percentage of subjects, total number of events, **and** incidence density ~~and event rate~~ will be presented by treatment group and overall at the SOC, ~~High Level Term~~ and Preferred Term (PT) level. Relative Risk ~~for each event~~ and its 95% CI ~~will~~**may** also be presented **on a**

targeted basis. The time to first occurrence of the specific events ~~and the time of the event with respect to the preceding dose of study medication~~ will be summarized.

All cause mortality will be summarized by treatment group and analyzed using *a Cox PH* model similarly as the primary endpoint.

All events sent to CEC (including TIAs) will be *summarized*. ~~grouped by type based on the standard MedDRA queries that correspond to cardiovascular and cerebrovascular events. Adjudication results will be summarized by event type and treatment group. A by subject listing of these events will be generated. The listing will include seriousness, severity, whether event is a reason for early study drug discontinuation or study withdrawal, and adjudication results.~~

Pancreatitis events will be adjudicated by the independent Pancreatitis Adjudication Committee. The information for investigator reported pancreatitis events and its adjudication results will be *summarized* ~~provided~~.

Section 8.3.6.5 Value Evidence and Outcomes Analyses

Original Text:

TRIM-D total score and score for each domain will be summarized descriptively by treatment group and scheduled visit. Score changes from baseline will be compared between treatments for each visit by ANCOVA an model.

Amended Text:

TRIM-D total score and score for each domain will be summarized descriptively by treatment group and scheduled visit. Score changes from baseline will be compared between treatments for each visit by an ANCOVA an model.

Section 11.2 Appendix 2: GSK Modified List of Highly Effective Methods for Avoiding Pregnancy in Females of Reproductive Potential (FRP), final listed item

Original text:

8. Male condom **combined with a female** diaphragm, with or without a vaginal spermicide (foam, gel, film, cream, or suppository). In the UK it is a country-specific requirement of the regulatory authority (Medicines and Healthcare Products Regulatory Agency) that a vaginal spermicide be used.

Amended text:

8. Male condom **combined with a female** diaphragm, with or without a vaginal spermicide (foam, gel, film, cream, or suppository). In the UK it is a country-specific

requirement of the regulatory authority (Medicines and Healthcare Products Regulatory Agency) that a vaginal ~~spermicide~~ **spermicide** be used.

Section 11.5.5 Reporting of SAEs to GSK, edit to second bullet, insertion of new third bullet

Original text:

- If the electronic system is unavailable for greater than 24 hours, the site will use the paper SAE data collection tool and fax it to the Medical Monitor or the SAE coordinator

Amended text:

- If the electronic system is unavailable for greater than 24 hours, the site will use the paper SAE data collection tool and fax it to the ~~Medical Monitor or the SAE coordinator~~ **safety designee as detailed in the Study Reference Manual**
- ***The investigator will be required to confirm review of the SAE causality by ticking the 'reviewed' box at the bottom of the eCRF page within 72 hours of submission of the SAE.***

TITLE PAGE

Division: Worldwide Development

Information Type: Protocol Amendment

| | |
|---------------|---|
| Title: | A long term, randomised, double blind, placebo-controlled study to determine the effect of albiglutide, when added to standard blood glucose lowering therapies, on major cardiovascular events in patients with Type 2 diabetes mellitus Harmony Outcomes Trial |
|---------------|---|

Compound Number: GSK716155

Development Phase: IV

Effective Date: 24-NOV-2014

Protocol Amendment Number: 1

Author (s): The protocol was developed by the members of the Executive Committee in conjunction with Duke Clinical Research Institute and the Sponsor.

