- TRIM-D, EQ-5D and study specific questionnaire (details in Section 6.3).
- TRIM-D is not required for subjects whose diabetes is treated by diet and exercise alone at Baseline.
- See Section 6.2.7.
- Only applies to women of child bearing potential. At screening perform urine pregnancy test. If positive, send serum sample to the central laboratory for confirmation. At Randomisation perform a urine pregnancy test. If result is positive do not randomize the subject. If the urine pregnancy test is negative then the subject can be randomised. If Screening and Randomisation are to take place at the same visit then follow the instructions for Screening. See Section 6.2.6.
- Study drug dispensing not performed at final visit, compliance check not performed at Randomisation

Section 6 Study Assessments and Procedures; insertion of the following table after Table 1

Table 7 Time and Events Table for Subjects Who Permanently Discontinue IP Prior to the End of the Study

| Procedures | Clinic visit as soon after permanent discontinuation of IP as possible | Phone Call 5 ± 1 week after last IP dose | Continue contact schedule established at randomisation 4 monthly ± 1 month. Telephone ^{1,2} | Continue contact schedule established at randomisation 4 monthly ± 1 month. Clinic visit ^{1,3} | Final study clinic visit ⁴ |
|---|--|--|--|---|---------------------------------------|
| Assessment of MACE and micro-vascular events | X | | X | X | X |
| HbA1c | X | | | X | X |
| Serum creatinine (eGFR) | X | | | X | X |
| Liver Function Tests (LFTs) ⁵ | X | | | X | X |
| Record available information on most recent lipid assessment ⁶ | X | | X (annually) | X (annually) | X |
| Patient reported outcomes questionnaire ⁷ | X | | | | |
| Key concomitant non-diabetes medication | X | X | X | X | X |
| Diabetes medication | X | X | X | X | X |
| Physical examination ⁸ | X | | | X | X |
| AEs leading to IP discontinuation | X | | | | |
| SAEs, AEs of special interest, | X | X | X | X | X |
| Study drug compliance | X | | | | |

1. After subjects permanently discontinue IP, follow-up should continue on the 4-monthly schedule established at randomisation.
2. Where a subject would have been scheduled to attend clinic at months 4, 12, 20, 28 etc after randomisation, a telephone contact will be performed instead (with assessments as shown above).

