6.3.1.2. EQ-5D

The EQ-5D will be self-administered by subjects in order to measure generic health status. Combining the EQ-5D with the disease-specific TRIM-D, which is designed to have maximum sensitivity to relevant aspects of disease related treatment, will provide a more robust evaluation of the impact of treatments for type 2 diabetes and allow for clearer interpretation of study results. TRIM-D results, if consistent with the general trends seen in the EQ-5D, will have enhanced credibility.

The EQ-5D is a standardized instrument used to evaluate generic health-related quality of life. It is applicable to a wide range of health conditions and treatments, and it provides a simple descriptive profile and a single index value for health status. It is also used to provide utilities, or preference weights, for use in economic (cost effectiveness) evaluations. It is available in 141 self complete official language versions.

The EQ-5D has been used extensively in studies to measure the impact of type 2 diabetes and treatments for the disease. A systematic review identified 54 publications reporting EQ-5D responses and 39 papers presenting evidence on the measurement properties of the EQ-5D in this population [Janssen, 2011]. This evidence supported the validity, reliability, and responsiveness of the EQ-5D for evaluating health-related quality of life in subjects with type 2 diabetes. Other studies reported that index scores from the EQ-5D have been shown to be an independent predictor of the risk of mortality, future vascular events, and other complications in people with type 2 diabetes [Clarke, 2009]. In addition, the SHIELD longitudinal study (1,741 respondents with type 2 diabetes and 4,543 without diabetes) used the EQ-5D to assess the 5-year changes in health-related quality of life in type 2 diabetes [Grandy, 2012].

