8.3.6.5. Value Evidence and Outcomes Analyses

TRIM-D total score and score for each domain will be summarized descriptively by treatment group and scheduled visit. Score changes from baseline will be compared between treatments for each visit by ANCOVA an model

For EQ-5D, subjects' responses at each visit for the 5 domains will be summarized categorically by treatment group, together with the summary of utility score at each visit and change from baseline by treatment group. Change from baseline will be compared between treatment groups for each visit by an ANCOVA model.

For study specific PRO questions, responses will be summarized descriptively by treatment group and scheduled visit.

Healthcare resource use will be summarized by treatment group and visit.

Further analysis details will be provided in the RAP.

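### Questionnaires stop after one visit once IP is permanently discontinued: this contradicts Section 6.3.1.1 for TRIM-D and Section 6.3.1.3 for the study-specific questions, and leaves the visit-wise EQ-5D comparison without most off-IP data

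*Protocol*

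**What the plan says.** Amendment 2 inserts into Section 6 a separate Time and Events Table for subjects who permanently discontinue IP. It has five columns: a clinic visit soon after stopping, a call about five weeks after the last dose, the continuing telephone contacts, the continuing clinic visits, and the final study visit. The questionnaire row reads "Patient reported outcomes questionnaire ⁷ | X"; the mark is in the first column and the other four are blank. Footnote 7 lists what the row covers: "7. TRIM-D, EQ-5D and study specific questionnaire (details in Section 6.3". Footnote 3 keeps the clinic visits at months 8, 16, 24, 32, "etc after randomisation, a clinic visit will be performed (with assessments as shown above". The physical examination row, by contrast, reads "Physical examination ⁸ | X | | | X | X", and HbA1c, creatinine and liver function tests follow the same pattern.

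The text on each instrument differs:

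- **TRIM-D** (Section 6.3.1.1 as amended): required from "all subjects at each 8 month visit (and, to the extent possible, at the time of study completion or withdrawal from the study". The only exception is at baseline, for subjects treated by diet and exercise alone.
- **EQ-5D** (Section 6.3.1.2): "The EQ-5D will be self-administered by subjects in order to measure generic health status". No visits are named.
- **Study-specific questions** (Section 6.3.1.3): three items, at a subset of sites, at baseline and every 8-month follow-up visit.

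Section 8.3.6.5 compares change from baseline in TRIM-D between arms by ANCOVA visit by visit. It does the same for EQ-5D: "Change from baseline will be compared between treatment groups for each visit by an ANCOVA model". The study-specific questions are only summarised descriptively, by arm and visit.

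**The concern.** A site with a subject off IP at a month-16 or month-24 visit has two instructions for TRIM-D and cannot follow both. If it follows the table, the questionnaire is missing by design, although the subject is in the clinic and has blood taken and an examination done.

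TRIM-D and EQ-5D are listed secondary endpoints, compared between randomised arms at each visit. Stopping IP is unlikely to be unrelated to health or treatment: Section 4.4.2 lists adverse events among the reasons, and Section 3.4.1.1 names gastrointestinal effects as an identified risk of albiglutide. A comparison that loses most off-IP values therefore drifts away from the randomised groups as follow-up lengthens. Section 3.3 says that subjects who stop drug are followed to the end of the study, and warns about bias from missing data in the primary comparison. The questionnaire schedule does not carry that principle through. An analysis plan can choose an estimand or a missing-data method, but it cannot recover answers that were never requested.

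**Working it through.** There is no stated figure to reproduce. The check is a comparison of texts, followed by an illustration of how many questionnaires are affected.

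**1. One subject traced through the schedule.** Suppose IP is stopped permanently at month 10 (an example). Questionnaires are collected at baseline, at month 8 under the main schedule, and at the visit just after stopping. At months 16, 24 and 32 and at the final visit, the discontinuation table schedules HbA1c, creatinine, liver tests and physical examination but no questionnaire. Section 6.3.1.1 schedules TRIM-D at months 16, 24 and 32, and where possible at completion.

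**2. Instrument by instrument, after stopping IP.**

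| Instrument | Discontinuation table | Text | Result |
|---|---|---|---|
| TRIM-D, 8-monthly | not collected | all subjects (6.3.1.1) | contradiction |
| TRIM-D, final visit | not collected | where possible (6.3.1.1) | weaker conflict |
| Study-specific questions, 8-monthly | not collected | every 8-month follow-up visit (6.3.1.3) | conflict |
| EQ-5D | not collected | no schedule in 6.3.1.2 | no contradiction, but the visit-wise comparison in 8.3.6.5 remains |

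**3. Is this only old text set against new?** No. The table and the revised sentence in 6.3.1.1 are both replacement wording of Amendment 2. Its summary of changes presents the table as a layout aid for visits already described in the text, and does not announce a cut in questionnaire collection.

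**4. Share of subjects with no scheduled questionnaire.** The protocol gives no IP discontinuation rate. For an assumed constant annual rate r, the share off IP at month m is 1 − (1 − r)^(m/12). For example, r = 10% and m = 24 gives 1 − 0.90² = 19.0%.

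| Assumed r per year | Month 8 | Month 16 | Month 24 | Month 32 |
|---|---|---|---|---|
| 5% | 3.4% | 6.6% | 9.8% | 12.8% |
| 10% | 6.8% | 13.1% | 19.0% | 24.5% |
| 15% | 10.3% | 19.5% | 27.8% | 35.2% |

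These shares are slightly too high for any visit at which the single post-discontinuation assessment is counted. They describe missing questionnaires, not bias.

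**5. Can the bias be sized?** Let p be the share off IP in an arm, and d the amount by which off-IP subjects score below on-IP subjects in that arm. The arm mean over all subjects is the on-IP mean minus p × d. An on-IP comparison therefore differs from the randomised comparison by (p × d) on albiglutide minus (p × d) on placebo. The protocol gives none of these four quantities, so no number is put on the bias. It is zero if the two products are equal.

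**The case against.** **Stopping TRIM-D can be defended.** It measures treatment satisfaction, with subscales such as treatment burden and compliance. Long after blinded drug has ended it mostly rates other therapy, so an on-treatment comparison plus one assessment at discontinuation is a legitimate choice. This stands as a design option, but the text does not make that choice: 6.3.1.1 says all subjects, and 8.3.6.5 carries no on-treatment limit. Nor does the argument extend to EQ-5D, which is a generic health measure.

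**The stakes are modest.** TRIM-D and EQ-5D are outside the gatekeeping and Hommel procedure of Section 8.3.5, and Section 6.3.1.4 says that cost is not an endpoint. Section 6.3.1.2 mentions utilities for economic evaluation as a general use of EQ-5D, not as an analysis planned in this trial. All of this stands.

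**Source.** The body text of Section 8.3.6.5 at hand is that of Amendment 1. The Amendment 2 change list touches only the TRIM-D sentence there, as a wording correction, so the EQ-5D comparison presumably carries over.

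**Stronger readings that the documents do not support.**

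- A reader might infer that 6.3.1.1 also requires EQ-5D of all subjects. It covers TRIM-D only.
- A reader might treat TRIM-D at study completion as an absolute duty. It is qualified as best effort.
- A reader might conclude that later comparisons contain only subjects on drug. One questionnaire is still taken after permanent discontinuation.
- A reader might want the per-visit ANCOVA replaced by a repeated-measures model. That is a preference; Section 8.3.6.5 leaves further detail to the analysis plan, and no model replaces uncollected data.

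**Conclusion.** The point holds as an inconsistency in the schedule with a consequence for secondary endpoints. For TRIM-D at the 8-monthly visits the contradiction is firm; at the final visit it is weaker. For the study-specific questions there is a conflict with 6.3.1.3, of descriptive importance only. For EQ-5D the fault is one of design: collection stops while the arms are still compared at each visit, so the later comparisons rest largely on subjects who have not permanently stopped IP.

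The number of questionnaires affected depends wholly on an unstated discontinuation rate; annual rates of 5% to 15% are assumed above only to show the range. The direction and size of any bias cannot be derived from the protocol. No primary or multiplicity-controlled claim is touched. It is still worth correcting, because the loss cannot be repaired at analysis and the visits already take place.

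**What to change.** In the discontinuation table, mark the questionnaire row in two more columns: the continuing 8-monthly clinic visit and the final study visit. EQ-5D should be included at the least, TRIM-D to agree with 6.3.1.1, and the study-specific questions, at the sites that use them, to agree with 6.3.1.3. The cost is a few minutes of self-completed questionnaire at visits already held. Subjects followed only by telephone would still have no questionnaire.

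If the intention is that TRIM-D applies only while subjects are on IP, leave it out after the discontinuation visit. In that case, limit 6.3.1.1 and the TRIM-D comparison in 8.3.6.5 explicitly to on-treatment data, and split the table row so that EQ-5D can continue. If the study-specific questions are also to stop, 6.3.1.3 needs the same limit.
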